8.1 Prior and concomitant therapy

Any medication which is considered necessary for the patient's welfare, and which is not expected to interfere with the evaluation of the study treatment, may be given at the discretion of the investigator. In general, patients should be closely monitored for side effects of all concomitant medications regardless of elimination path, especially those with narrow therapeutic indices, such as warfarin, phenytoin, quinidine, carbamazepine, phenobarbital, cyclosporine, and digoxin. From signing of consent for full study to safety follow-up visit, all concomitant medications (including start/stop dates, dose, frequency, route of administration and indication) must be recorded in the patient's source documentation, as well as on the appropriate pages of the CRF. At prescreening and during active follow-up period, only concomitant medications that are administered to treat AEs related to study-specific procedures are mandatory to be reported. Administration of contrast media for protocol-specified radiological procedures (CT scan or MRI) does not need to be reported on the concomitant medication CRF page, unless there is an AE related to the contrast medium injection (e.g. allergic reaction).

Prohibited prior and concomitant therapies and permitted concomitant therapies are listed in **Table 2-8** and **Table 2-9**, respectively.

Table 2-8 Prohibited prior and concomitant therapies

Prohibited prior and concomitant therapy (see also Section 6.2)	Time period when	Comments prohibited
Prohibited for all patients		
Anetumab ravtansine (or any other mesothelin-based therapy)	Prior to study treatment	
Other systemic anticancer treatment (except study treatment) (cytotoxic therapy, targeted therapies, immunotherapy, hormonal therapy, or any other experimental or approved therapy)	Prior to study treatment until safety follow-up visit	
Use of biologic response modifiers, such as G-CSF	Within 6 weeks before the start of study treatment	G-CSF and other hematopoietic growth factors may be used during the study in the management of acute toxicity such as febrile neutropenia when clinically indicated per ASCO Recommendations for Therapeutic Use of CSF (26) or at the discretion of the investigator or according to local label guidance (if medically necessary, growth factors may be administered at recommended doses no earlier than 24 h after and not in the 24 h before anetumab ravtansine administration; see also (27); however they may not be substituted for a required dose reduction).
Blood transfusions and chronic therapy with IV or subcutaneous erythropoietin-stimulating agents (epoetin alpha, darbepoetin alpha)	Within 6 weeks before the start of study treatment. Thereafter, they are allowed per institution guidelines but may not be used as substitute for a required dose reduction.	Patients receiving chronic low-dose erythropoietin for chronic renal failure are allowed provided no dose adjustment is undertaken within 6 weeks before signing consent for full study and until safety follow-up visit and provided that they fulfill conditions of inclusion criterion number 7 and exclusion criterion number 18.
Platelet transfusions	Within 3 weeks before the start of study treatment. Thereafter, they may not be used as substitute for a required dose reduction.	
Anti-arrhythmic therapy other than beta blockers or digoxin		
Acute steroid therapy or taper		Chronic steroid therapy is acceptable, provided that the dose is stable for 1 month before the start of study treatment and thereafter.
Radiotherapy	Within 4 weeks before the start of screening for full study	Except for pain control, see below in Table 2-9. Patients must have recovered from all therapy-related toxicities. The site of previous radiotherapy should have evidence of PD if this is the only site of disease: measurable pleural disease should be assessed on a contrast enhanced CT/MRI done at

Clinical Study Protocol

19-September-2018

BAY 94-9343 (Anetumab in Pancreatic Cancer)
Version 4.0

Page: 38 of 77

Prohibited prior and concomitant therapy (see also Section 6.2)	Time period when	Comments prohibited
		the minimum 4 weeks after the end of RT and compared with previous imaging; unequivocal progression should be judged by the investigator as per mRECIST per MPM.
Drugs with known bone marrow toxicity		
Strong inhibitors and strong inducers of CYP3A4 (listed in Appendix 16.5), including: - Herbal preparations containing CYP3A4 inducers (e.g. St John's Wort) - Grapefruit and grapefruit juice (CYP3A4 inhibitor)	Within 2 weeks before the start of study treatment until the safety follow-up visit	DM4 is a substrate of CYP3A4. During study treatment, moderate and weak CYP3A4 inducers should be used with caution as decrease in plasma concentrations of DM4 cannot be ruled out.

ASCO = American Society of Clinical Oncology; CSF = Colony stimulating factor; CT = Computed tomography; CYP3A4 = Cytochrome P450, family 3, subfamily A, polypeptide 4; DM4 = Derivatives of maytansine 4; GCSF = Granulocyte-colony stimulating factor; IV = Intravenous; MPM = Malignant pleural mesothelioma; mRECIST = Modified Response Evaluation Criteria in Solid Tumors; MRI = Magnetic resonance imaging; PD = Progressive disease; RT = Radiotherapy

Table 2-9 Permitted concomitant therapies

Permitted concomitant therapies	Comments
Permitted for all patients	
Oral and parenteral anti-coagulant agents, e.g. heparin, enoxaparin, warfarin, rivaroxaban, dabigatran, apixaban or aspirin at a dose ≤ 100 mg	Allowed if continued maintenance therapy is necessary at the investigator's discretion and provided that they fulfill conditions of inclusion criterion number 8 (Section 6.1.2).
Institutional standards for the management of infusion reactions	May be utilized at the discretion of the investigator. Pre-treatment with anti-nausea medication is allowed at the investigators discretion. See anti-emetic note below.
Palliative radiotherapy for pain control	Allowed provided that: 
 - In the opinion of the investigator, the patient does not have PD, - No more than 10% of the patient's bone marrow is irradiated, - The radiation field does not encompass a non-pleural target lesion or a pleural measurable lesion, - The radiation field does not encompass a lung field (to reduce the risk for interstitial lung disease [ILD] caused by irradiation pneumonitis), and - Anetumab ravnansine administration is interrupted during radiotherapy. Study treatment can be restarted after end of radiotherapy, provided all requirements outlined in Section 7.3 of this protocol are taken into account. The maximum interruption period for both drugs should not be exceeded.

Permitted concomitant therapies	Comments
Standard therapies for concurrent medical conditions	
Prophylactic standard anti-emetics	May be administered according to standard practice: dexamethasone plus 5-HT3 blockers, such as granisetron, ondansetron, or an equivalent agent, are allowed on “as needed” basis.
Treatment with non-conventional therapies (for example herbs, except St John’s Wort, or endpoints, in the opinion of the	investigator. acupuncture), and vitamin/mineral supplements Acceptable provided that they do not interfere with the study
Bisphosphonates or denosumab, with supplement of calcium and vitamin D	
Palliative (e.g. analgesics) and supportive care (e.g. nutritional therapy) for other disease-related symptoms and for toxicity associated with treatment	
Strong P-gp inhibitors (e.g. amiodarone, azithromycin, captopril, carvedilol, clarithromycin, conivaptan, cyclosporine, diltiazem, dronedarone, erythromycin, felodipine, itraconazole, ketoconazole, lopinavir and ritonavir, quercetin, quinidine, ranolazine, ticagrelor, verapamil)	DM4-Me (metabolite of DM4) is a P-gp substrate. Caution should be exercised with concomitant administration of strong P-gp inhibitors. If anetumab ravtansine must be co-administered with a strong P-gp inhibitor, then the patient should be carefully monitored or the strong P-gp inhibitor replaced at investigator’s discretion.
Narrow therapeutic index medications	Patients taking narrow therapeutic index medications should be monitored proactively, if these medications cannot be avoided.
Beta blockers or digoxin	Permitted for patients with cardiac arrhythmias requiring therapy

5-HT3 = 5-hydroxytryptamine (serotonin); DM4 = Derivatives of maytansine 4; DM4-Me = Methyl-DM4; ILD = Interstitial lung disease; PD = Progressive disease; P-gp = Permeability glycoprotein

All prior anti-cancer therapies, and all concomitant therapies including ophthalmological therapies as of full screening will be recorded on the CRF. At prescreening and during active follow-up period, only concomitant medications that are administered to treat AEs related to study-specific procedures are mandatory to be reported.

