6.2 Exclusion criteria

Patients who meet the following criteria at the time of full screening and on C1D1 will be excluded:

1. Previous assignment to treatment during this study. Patients permanently withdrawn from study participation will not be allowed to re-enter the study.
2. Previous (within 5 drug half-lives – if drug half-life in subjects is known – or 28 days, whichever is shorter, before the start of study treatment) or concomitant participation in another clinical study with investigational medicinal product(s) (IMP[s]).
3. Patients with corneal epitheliopathy or any eye disorder that may predispose the patients to this condition at the discretion of the investigator.
4. Previous or concurrent cancer that is distinct in primary site or histology within 5 years. Exceptions: curatively treated
 - Cervical cancer *in situ*.

- Non-melanoma skin cancer.
 - Superficial bladder tumors (Non-invasive tumor [Ta], Carcinoma *in situ* [Tis] and Tumor invades lamina propria [T1]).
5. Major surgery, open biopsy or significant traumatic injury within 28 days before the start of study treatment.
 6. Pregnant or breast-feeding patients. WOCBP must have a serum pregnancy test performed a maximum of 7 days before the start of study treatment, and a negative result must be documented before the start of study treatment.
 7. Pre-existing cardiac conditions as outlined below:
 - Congestive heart failure \geq New York Heart Association (NYHA) class 2 (specified in Appendix 16.2).
 - Unstable angina (angina symptoms at rest), new-onset angina (begun within the last 3 months). Myocardial infarction less than 6 months before the start of study treatment.
 - Cardiac arrhythmias requiring anti-arrhythmic therapy (beta blockers or digoxin are permitted).
 8. Clinically significant uncontrolled hypertension (systolic blood pressure $>$ 150 mmHg or diastolic pressure $>$ 90 mmHg despite optimal medical management).
 9. Arterial thrombotic or embolic events such as cerebrovascular accident (including transient ischemic attacks), or venous pulmonary embolism within 6 months before the start of study treatment; venous thrombotic events such as deep vein thrombosis within 3 months before the start of study treatment.
 10. Ongoing or active infection (bacterial, fungal, or viral) of NCI-CTCAE version 4.03 Grade $>$ 2.
 11. Known history of human immunodeficiency virus (HIV) infection.
 12. Known history of chronic hepatitis B or C.

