 13. Patients with seizure disorder requiring medication.
 14. Symptomatic brain metastases or meningeal tumors or other uncontrolled metastases in the central nervous system (CNS) unless the patient
 - Is $>$ 6 months from definitive therapy,
 - Has a negative imaging study within 4 weeks before study entry (ICF signature for full study) and
 - Is clinically stable with respect to the tumor at the time of study entry.
 15. History of organ allograft, stem cells or bone marrow transplant.
 16. Patients with evidence or history of bleeding diathesis. Any hemorrhage or bleeding event \geq CTCAE Grade 3 within 4 weeks before the start of study treatment.
 17. Non-healing wound, ulcer, or bone fracture.
 18. Renal failure requiring peritoneal dialysis or hemodialysis.

19. Known hypersensitivity to anetumab ravtansine, study drug classes or excipients in the formulation.
20. Any illness or medical conditions that are unstable or could jeopardize the safety of the patient and his/her compliance in the study.
21. Unresolved toxicity higher than NCI-CTCAE version 4.03 Grade 1 attributed to any prior therapy/procedure excluding anemia or neuropathy Grade 2 (see Section 6.1.2, inclusion criterion 8) and alopecia of any Grade.
22. Any prohibited prior or concomitant therapy (see **Table 2-8** in Section 8.1).

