- Patient starts treatment with any other anti-cancer therapy or any other prohibited medication as per Section 8.1.
- Positive serum β -HCG test consistent with pregnancy. Pregnancy should be reported along the same timelines as an SAE.
- Use of illicit drugs or other substances that may, in the opinion of the investigator or his designated associate(s), have a reasonable chance of contributing to toxicity or otherwise confound the results.
- Development of any intercurrent illness or situation which may, in the judgment of the investigator, affect assessments of clinical status and study endpoints to a relevant degree.
- Lost to follow-up.
- Death.

Patients must be withdrawn from **treatment with anetumab ravtansine** if any of the following occurs:

- CTCAE Grade 4 non-hematological AE and Bayer Grade 4 corneal toxicity (see Table 2-6) (except at the investigator's discretion in case of certain Grade 4 abnormality of laboratory assessments, such as abnormal laboratory assessments without corresponding clinical symptoms, or abnormal laboratory assessments that can be easily clinically managed).
- If any type of TEAE requiring dose modification does not resolve to Grade ≤ 1 (or Hb ≥ 8 g/dL in case of anemia) within 6 weeks after the last dose of anetumab ravtansine.
- Delay in anetumab ravtansine administration of 3 weeks (max. 6 weeks between 2 infusions of study drug).
- TEAE requiring dose reduction when already at the 4.5 mg/kg Q3W dose level (minimum dose).
- More than 2 dose reductions required due to a TEAE.

AE = Adverse event; β -HCG = β subunit of human chorionic gonadotropin; CTCAE = Common Terminology Criteria for Adverse Events; Hb = Hemoglobin; RECIST = Response Evaluation Criteria in Solid Tumors; PD = Progressive disease; Q3W = Every 3 weeks; SAE = Serious adverse event; TEAE = Treatment-emergent adverse event

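### The Table 2-9 row on strong P-gp inhibitors permits, with monitoring, five entries that Table 2-8 prohibits as strong CYP3A4 inhibitors, and three anti-arrhythmics that Table 2-8 also bars

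*Combined protocol and SAP*

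**What the plan says.** Section 8.1 sends the reader to Table 2-8 for prohibited therapies and to Table 2-9 for permitted ones.

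- **Table 2-8, CYP3A4 row.** It prohibits "Strong inhibitors and strong inducers of CYP3A4 (listed in Appendix 16.5", for the period "Within 2 weeks before the start of study treatment until the safety follow-up visit". The reason given is that DM4 is a CYP3A4 substrate.
- **Table 2-8, anti-arrhythmic row.** It prohibits anti-arrhythmics for all patients, apart from beta blockers and digoxin.
- **Table 2-8, steroid row.** It prohibits "Acute steroid therapy or taper" and excepts only chronic use at a stable dose.
- **Table 2-9, P-gp row.** Under a heading that extends the permissions to every patient, it names strong P-gp inhibitors as examples. It asks for caution because DM4-Me is a P-gp substrate. If such a drug has to be given, the patient is to be monitored, or the drug replaced if the investigator so decides.
- **Table 2-9, infusion-reaction and anti-emetic rows.** The first says "Pre-treatment with anti-nausea medication is allowed at the investigators discretion" and points to the second, under which "dexamethasone plus 5-HT3 blockers, such as granisetron, ondansetron, or an equivalent agent, are allowed" as needed.

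Two other places depend on these tables. Exclusion criterion 22 in Section 6.2 is "Any prohibited prior or concomitant therapy", with a pointer to Table 2-8. Figure 2-1 in Section 6.3.2 requires withdrawal from study treatment if: "Patient starts treatment with any other anti-cancer therapy or any other prohibited medication as per Section 8.1".

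**The concern.** A concomitant-medication table is used at the bedside, often one row at a time. A clinician who wants to give clarithromycin or itraconazole will find it by name in the P-gp row of Table 2-9, with an instruction to monitor. That row speaks only of P-gp and DM4-Me. Nothing in it warns that the same drug is barred on CYP3A4 grounds by the preceding table.

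Two things are at stake. The first is an avoidable interaction that the protocol itself meant to prevent. Section 3.1 shows little room at the study dose: 6.5 mg/kg is the maximum tolerated dose, 7.5 mg/kg was not tolerated, and at 6.5 mg/kg 16 of 32 patients needed a dose reduction and 12 of 32 had corneal toxicity. The second is consistency among the two or three centers. One site may treat co-administration as allowed. Another may record a deviation, or apply the Figure 2-1 withdrawal rule.

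**Working it through.** The plan has no figure to reproduce on this point. The check compares the lists and looks for a rule of precedence.

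**Inputs.** The P-gp row of Table 2-9 has 19 entries, taking lopinavir and ritonavir as one. The strong CYP3A4 inhibitor column of Appendix 16.5 has 17 entries, including lopinavir/ritonavir as a pair and ritonavir alone.

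**Step 1: overlap with the CYP3A4 prohibition.**

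| Entry | Table 2-9, P-gp row | Appendix 16.5, prohibited through Table 2-8 |
|---|---|---|
| Clarithromycin | permitted with monitoring | strong inhibitor |
| Conivaptan | permitted with monitoring | strong inhibitor |
| Itraconazole | permitted with monitoring | strong inhibitor |
| Ketoconazole | permitted with monitoring | strong inhibitor |
| Lopinavir/ritonavir | permitted with monitoring | strong inhibitor |

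Overlap: 5 of 19 entries, 5/19 = 26.3%. Counting lopinavir and ritonavir as separate substances gives 6 of 20.

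**Step 2: overlap with the anti-arrhythmic prohibition.** The same row lists amiodarone, dronedarone and quinidine. The protocol does not label them as anti-arrhythmics; that is ordinary drug classification and is taken here as an assumption. None is a beta blocker or digoxin, so used for that purpose they fall under the Table 2-8 prohibition. This adds 3 entries: 5 + 3 = 8 of 19, 8/19 = 42.1%.

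**Step 3: is there a carve-out or a precedence rule?** Elsewhere the tables show how an exception is written. The radiotherapy row of Table 2-8 excepts pain control and refers to Table 2-9. The herbal row of Table 2-9 leaves out St John's Wort, in line with the CYP3A4 prohibition. The P-gp row has no such wording, and no general statement in Section 8.1 says which table controls.

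**Step 4: would a simple rule that Table 2-8 prevails work everywhere?** It gives the right answer for all eight entries. Radiotherapy for pain, and beta blockers or digoxin, are already excepted inside Table 2-8. Anti-emetic dexamethasone is the exception: Table 2-9 allows it by name, but the Table 2-8 steroid row does not except it. A precedence line therefore has to come with an exception in that row.

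**Step 5: size.** The counts describe text. The documents give no frequency of use of these drugs, no change in DM4 exposure and no rate of resulting withdrawals, so nothing can be computed per patient.

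**The case against.** The best defense is that the two rows deal with different mechanisms, CYP3A4 for DM4 and P-gp for DM4-Me, and that a drug may be restricted under both. On that view an absolute, dated prohibition naturally controls over a list of examples that itself urges caution. Other criteria narrow the exposure further. Known HIV infection is excluded (criterion 11), which makes lopinavir/ritonavir largely theoretical, and arrhythmias needing drugs other than beta blockers or digoxin are excluded at entry (criterion 7). All of this lowers the practical risk. It does not remove the conflict, because the row sits among permissions, names the drugs and leaves the choice to the investigator. Nor do entry criteria settle what is given for an infection or a new arrhythmia during treatment.

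A reader might infer two stronger points, which the documents do not support.

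- **That the steroid rows are a contradiction of the same kind.** Exclusion 22 cites Table 2-8, and the lead-in to Section 6.2 reads "Patients who meet the following criteria at the time of full screening and on C1D1 will be excluded", so dexamethasone before the first infusion could be said to exclude the patient. But Table 2-9 names dexamethasone for this purpose, and the anti-nausea note points to it; Section 15 records that note as a clarification in Version 4.0. The natural reading is a specific exception to a general row. The period cell of the steroid row is empty in the available text, which may be a layout loss, and the mention of the time after treatment start concerns the stability of chronic doses. Figure 2-1 refers to Section 8.1 as a whole, which contains the permission. Corticosteroids after infusion reactions (Section 7.3.2.3) and steroid eye drops (Table 2-6, Section 9.5.3.7) are plainly provided for.
- **That phenytoin and carbamazepine are also permitted against the prohibition.** Both are named in Section 8.1 among drugs with a narrow therapeutic index, and both are strong inducers in Appendix 16.5. The Section 8.1 sentence is an instruction to monitor, the matching Table 2-9 row names no drug, and exclusion 13 removes patients with a seizure disorder requiring medication.

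**Conclusion.** The inconsistency is real and is in the current text. Five entries in the Table 2-9 P-gp row are prohibited by Table 2-8 and Appendix 16.5 on DM4-interaction grounds. Three more fall under the anti-arrhythmic prohibition, for which Table 2-8 gives no reason and, in the available text, no period. The CYP3A4 part needs no interpretation. The anti-arrhythmic part rests on the usual classification of the three drugs.

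Severity is minor. The consequence is a possible avoidable interaction and uneven decisions between sites. It would be wrong to infer an effect on the primary endpoint. The documents show none, and under Section 6.3.2 a patient taken off study treatment is still followed for the study objectives. The two-stage design and its decision limits are untouched.

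**What to change.** At the next amendment:

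1. In the P-gp row of Table 2-9, delete clarithromycin, conivaptan, itraconazole, ketoconazole, lopinavir/ritonavir, amiodarone, dronedarone and quinidine, or mark each *prohibited, see Table 2-8*.
2. Add to Section 8.1: *Permission under Table 2-9 does not override a prohibition in Table 2-8 unless stated.* The P-gp list gives examples only, so this line also covers drugs it does not name.
3. So that item 2 does not bar steroid use that the protocol provides for, add to the Table 2-8 steroid row: *Except anti-emetic dexamethasone (Table 2-9), corticosteroids for infusion/hypersensitivity reactions (Section 7.3.2.3) and topical ocular steroids (Table 2-6).*

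Exclusion 22 and Figure 2-1 can stay as they are. The cost is eight deletions or marks and two added sentences, with no extra procedures, patients or analyses.

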8.2 Post-study therapy

At the end of study treatment, further therapy is at the discretion of the investigator.

No results are available from human interaction studies between anetumab ravtansine and other chemotherapies. No data are available to evaluate the potential interaction between anetumab ravtansine and radiation treatment. Therefore, when administering these agents after study treatment is withdrawn, it should be taken into consideration that anetumab ravtansine, DM4 or DM4-Me levels may be detectable for several weeks and could interact with chemotherapy and radiotherapy including palliative radiotherapy as outlined in **Table 2-9** following discontinuation of anetumab ravtansine.

Clinical Study Protocol

19-September-2018

BAY 94-9343 (Anetumab in Pancreatic Cancer)
Version 4.0

Page: 41 of 77

Day Cycle	Pre-Screening	Screening ^c	1	8	15	1	8	15	EOT ^d	Active FU ^o	LTFU (every 3 months)
			1	1		2+	2 and 3 only	2 and 3 only			
Electrolyte and Chemistry Panel ^a		x	x	x	x	x	x	x	x		
Coagulation Panel ^a		x				x					
Serum pregnancy test (WOCBP only)		x	Every 6 weeks until EOT						x		
Dipstick Urinalysis		x	x			x					
Serum CEA, CA19-9 ^g			x			x					
AE Evaluation	x ^m	x	x	x	x	x	x	x	x	x	
Radiologic Evaluation ^b		x	x ^b							x ^b	
Echocardiogram/ MUGA ^h		x				x ^h					
Ophthalmologic Exam ⁱ		x	x			x			x		
Archival or Fresh Tumor Tissue for mesothelin expression testing ^k	x										
Research specimens for mesothelin and exploratory analysis (biomarkers)			x			x ^p			x		
Survival Follow- Up											x

ALL VISITS AND PROCEDURES WILL BE PERFORMED WITHIN 48 HOURS (+/- 1 day) WINDOW
UNLESS OTHERWISE SPECIFIED.

^a Complete blood count with differential. Electrolyte and Chemistry panel includes amylase, albumin, alkaline phosphatase (ALP), bicarbonate, total bilirubin, direct bilirubin, urea or BUN, calcium, chloride, creatinine, eGFR, gamma-glutamyl transferase (GGT), glucose, lactic dehydrogenase (LDH), lipase, phosphorus, potassium, total protein, AST, ALT, sodium, and uric acid. Specific assessments to be run per visit are detailed below. Coagulation tests including PTT and INR or PT.

^b Contrast-enhanced CT or MRI of chest/abdomen/pelvis or PET/CT will be done every 6 weeks for the first 6 months after the start of treatment, or more frequently if clinically indicated, every 9 weeks until the end of year 2 and every 12 weeks thereafter until disease progression or end of study, whichever comes first. To be done in +/- 7 days.

^c Screening procedures are to be completed within 7 days of treatment initiation unless otherwise specified below. CT or MRI c/a/p scans will be done within 28 days of treatment. An ophthalmologic examination will be done within 3 weeks before the start of study treatment.

^d Treatment will be continued until disease progression, intolerable toxicities or withdrawal. End of treatment (EOT) visit will occur 30 days (+/- 7 days) after treatment discontinuation.

^e Vital signs will include measurement of weight, blood pressure, heart rate, temperature, and respiratory rate. Height to be done at baseline only or at Cycle 1 Day 1 prior to the first dose of study drug.

^f Includes medical, surgical and prior cancer treatment history.

^g CEA and CA 19-9 will be checked every 3 weeks during the treatment period including on day 1 of cycle 1 and in follow up until progression

^h Echocardiogram or MUGA to be done at baseline, C2D1, C4D1 (+/- 7 days) and as clinically indicated thereafter.

ⁱ Ophthalmology exam as below every cycle.

^j All prior anti-cancer therapies and all concomitant therapies including ophthalmological therapies. At prescreening and during active follow-up period, only concomitant medications that are administered to treat adverse events related to study-specific procedures are mandatory to be reported.

^k Archival tissue is preferred and fresh biopsy should only be obtained if no archival tissue is available and if in the investigator's judgement, there is no additional risk for the patient's safety.

^l 12-lead ECG to be done at screening, C1D1, C2D1, C3D1, C4D1, C5D1, C6D1, and EOT.

^m At prescreening, only adverse events that are related to study-specific procedures are mandatory to be reported.

ⁿ Prior to first dose of study drug.

^o Patients who discontinue study treatment due to any other reason than confirmed radiological PD will continue clinic visits during active follow-up for efficacy assessments including tumor response. These assessments will continue until disease progression, consent withdrawal, lost to follow-up or end of study.

^p Biomarker plasma for exploratory analysis will be done at C6D1 (+/- 1 cycle).

